5.4.3 Multiple imputation sensitivity analyses steps

The following steps are followed in order to create the structure of the analysis dataset where missing values and appropriate variables could be imputed.

- Obtain subject id, treatment group, stratification factor, sex, race group, age group, BMI group (subjid trt01pn mmstratn sexn race agedmedn bmimedn) from ADBS, ADSL.
- Obtain number of prior migraine prophylactic treatment failed, baseline disease duration group (prophfln durmedn) from ADBS.
- Obtain avisitn paramcd param aval avalc base chg dtype from ADATTACK
- If dtype='BOCF' then expect to obtain aval=. and chg=.
- Ensure the baseline values are included in the chg variables before data transformation, eg if avisitn=2000 is baseline then chg=base; Number of prior migraine prophylactic medication failed (prophfln) should be a dichotomous variable. Therefore, if prophfln gt 3 then prophgrp=1; otherwise prophgrp=0.
- Transpose all the data so you have one observation per subject and each visit becomes a variable within its own right, eg rows where avisitn=2004, 2008, 2012 become the column week4, week8, week 12.
- Impute the missing data for MAR and MNAR separately according to the methods in next steps

MAR multiple imputations steps:

Note that the some variable has missing values and there is a mix of categorical and continuous variables in the modelling of the missing data. Therefore, fully conditional specification (FCS) methods are employed within proc mi to impute the missing data.

- FCS logistic is used for dichotomous variables (mmstratn sexn agemedn bmimedn prophgrp durmedn); discrim is used for categorical variables with more than 2 categories (race); regpmm is used for continuous variables (wk0, wk4, wk8, wk12).
- wk4, wk8 and wk12 represent the chg variable for each of the visits respectively, and wk0 is baseline.

MNAR multiple imputations steps:

- Here is an implementation of the pattern-mixture model approach that uses a control-based pattern imputation and imputing the missing data step-by-step, where the baseline variables inform on any missing baseline efficacy values. The baseline efficacy values then inform on the next visit, which then informs on the next visit and so on until all visits have non-missing data.
- Furthermore, an option is used at post-baseline visits (modelobs= (trt01pn='0')), assuming the treatment code for placebo is 0) to include an adjustment for the fact that any missing data from active treatment subjects will be similar to placebo subjects under the assumption that missing values in the active treatment subjects implies they are no longer on treatment. That is, an imputation model for the missing data in the active treatment group is constructed not from the observed data in the active treatment group but rather from the observed data in the placebo group. This model is also the imputation model that is used to impute missing data in the placebo group.

MAR and MNAR modeling step:

- For the primary endpoint, first, define 50% Responders based on imputed MMD data under the assumption of MAR or MNAR. Then, use the same method as for primary variable - the stratified CMH test to get estimates for numbers of responders in each treatment group and odds ratio at week 12 for each dataset..
- For change from baseline in MMD it is used a linear mixed effects model on imputing data under the assumption of MAR or MNAR. There is no gaps in imputed data, therefore, all the data is available to analyze and can use a fixed effects model looking only at the avisitn=2012/week12 data.

MAR and MNAR combining step:

- The output dataset with the treatment LS means (LSMEANS) and the treatment differences (DIFF) are then sorted, manipulated and read into proc mianalyze to combine the individual sets of imputed results into one set of overall results, see all steps SAS codes in TFLs document.

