2.5.3 Sensitivity analyses

In order to assess the robustness of the analysis for primary endpoint during the double-blind treatment epoch, next analyses will be done:

1. Without any imputation for missing data, a generalized linear mixed model (GLMM) which account for temporal variability will be used.
2. Logistic regression analysis will be used to get odds ratio of AMG 334 vs placebo in the 50% response rate after the missing data are imputed as non-response.
3. Stratified CMH test will be repeated based on multiple imputation with assumption of MAR and MNAR.

In all cases, the odds ratio of treatment group compared to placebo group with associated 95% confidence intervals and p-values will be provided.

All details of models descriptions are in [Section 5.4.1](#).

To address the impact of missing data on primary efficacy analysis, the amount of missing data, the distribution of missing data among treatment groups, and the reasons for missing data will be examined. If substantial amount of missing data is observed or if imbalance occurs amongst the treatment groups, additional sensitivity analyses, including those based on alternative missing data assumptions, will be performed as deemed appropriate and necessary.

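### SAP 5.4.3 does not say how treatment enters the MAR multiple imputation; read literally it pools the arms and slightly dilutes the MAR sensitivity analyses

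*SAP*

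**What the plan says.** SAP 2.5.3 lists, as one of three sensitivity analyses of the primary endpoint: "Stratified CMH test will be repeated based on multiple imputation with assumption of MAR and MNAR". SAP Table 5 and the modelling step in 5.4.3 apply the same imputations to change in monthly migraine days (MMD).

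SAP 5.4.3 sets out the steps. The dataset is built first: "Obtain subject id, treatment group, stratification factor, sex, race group, age group, BMI group (subjid trt01pn mmstratn sexn race agedmedn bmimedn"). The grouped number of failed prophylactics, the disease-duration group and the visit values are then added. The MAR step assigns a fully conditional specification (FCS) method to each variable type:

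- dichotomous: "FCS logistic is used for dichotomous variables (mmstratn sexn agemedn bmimedn prophgrp durmedn");
- categorical and continuous: "discrim is used for categorical variables with more than 2 categories (race); regpmm is used for continuous variables (wk0, wk4, wk8, wk12").

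Treatment appears in neither list. It is named in the missing-not-at-random (MNAR) step, where "an option is used at post-baseline visits (modelobs= (trt01pn='0")) restricts the post-baseline imputation models to placebo data. For the programs the section says: "see all steps SAS codes in TFLs document".

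**The concern.** An imputation model should contain every variable that the later analysis compares. If treatment is left out, a missing Week 12 value in the active arm is predicted from a relation averaged over both arms, so it is drawn towards placebo, and a missing placebo value is drawn towards active. The treatment difference in the completed data is too small.

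Treatment cannot be assumed to be off the list only because it is never missing. The randomisation stratum is never missing and is listed. The baseline value `wk0` is also listed, although SAP 5.1.5 says every patient in the full analysis set (FAS) will have baseline rates. The list therefore reads as the imputation model, not as the subset of variables that need filling in.

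What is at stake is whether the MAR analysis is a like-for-like check. The GLMM for the primary endpoint (SAP 5.4.1) and the mixed model for change in MMD (SAP 2.6.2) both carry treatment and treatment by visit. A MAR imputation without treatment rests on a stricter assumption: that treatment has no effect at Week 12 beyond what the earlier visits and baseline covariates already convey.

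**Working it through.** **Inputs from the documents.** Response 18% on placebo and 38% on active, 110 per arm, two-sided 0.05, 90% power (SAP 3; Protocol 9.8). Allocation 1:1 (SAP 1.1.3). FAS patients have at least one post-baseline monthly value (SAP 2.2). Non-completion of the double-blind epoch: 246 randomised, 242 completed (Protocol, Amendment 3 rationale), so 4/246 = 1.6%. The SAP calls more than 20% missing high (SAP 5.1.6), which sets the top of the range.

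**Assumptions, not in the documents.** Visit values are normal with unit variance and equal correlation ρ between visits, with ρ = 0.5 or 0.7. The treatment shift is the same at each visit. Data are missing at random with the same share m in each arm. Linear regression stands in for predictive mean matching.

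**The plan's own figure.** With 110 per arm, power for 18% against 38% is 91.6%, and the odds ratio is (0.38/0.62)/(0.18/0.82) = 2.79. Both agree with the stated 90% and 2.8. This only anchors the rates; the sample size is not in question.

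**Pooled imputation in closed form.**

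1. Shift between arms: d = Φ⁻¹(0.38) − Φ⁻¹(0.18) = −0.305 + 0.915 = 0.610.
2. Pooling the arms 1:1 adds c = d²/4 = 0.093 to every variance and covariance.
3. With k earlier visits observed, the pooled slope on each is b = (ρ + c)/[1 + c + (k − 1)(ρ + c)]. The imputed arm means differ by k·b·d instead of d.
4. The within-arm variance of an imputed value is v = k·b²·[1 + (k − 1)ρ] + (1 + c) − k·b·(ρ + c).
5. Responders are values below 0. The arm means lie 0.305 either side of 0.610, and imputation shrinks that distance by k·b.

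Example, k = 2, ρ = 0.5: b = 0.593/1.686 = 0.352 and k·b = 0.703; v = 0.371 + 1.093 − 0.417 = 1.047. Active: Φ[−(0.610 − 0.703 × 0.305)/√1.047] = 34.9%. Placebo: Φ[−(0.610 + 0.703 × 0.305)/√1.047] = 21.0%. The imputed patients therefore show a 13.9-point difference in place of 20, and the overall loss is m × 6.1 points.

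Loss in points on the 20-point difference:

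| Missing at Week 12 | Weeks 4 and 8 observed, ρ = 0.7 | Weeks 4 and 8 observed, ρ = 0.5 | One earlier month only, ρ = 0.7 | One earlier month only, ρ = 0.5 |
|---|---|---|---|---|
| Imputed difference | 16.7 | 13.9 | 14.4 | 10.7 |
| 1.6% | 0.05 | 0.10 | 0.09 | 0.15 |
| 5% | 0.16 | 0.30 | 0.28 | 0.46 |
| 10% | 0.33 | 0.61 | 0.56 | 0.93 |
| 20% | 0.65 | 1.21 | 1.12 | 1.86 |

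Simulation of the same set-up gives 0.05-0.2, 0.2-0.5, 0.4-0.9 and 0.6-1.8 points in turn, within 0.1 of the closed form. With treatment in the imputation model the simulated difference stays at about 20 points and the odds ratio at about 2.8 for every missing share tried.

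**Change in MMD.** On a mean scale the share of the treatment difference lost is m × (1 − k·b). Here k·b runs from 0.543 (one month, ρ = 0.5) to 0.841 (two months, ρ = 0.7). The loss is thus 0.8% to 2.3% of the difference at 5% missing, and 3.2% to 9.1% at 20%.

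**The case against.** The strongest reply is that the text never says the arms are pooled. The sentence assigns methods to variable types and does not present itself as a full model statement. A run by arm, which is the natural remedy, would produce exactly this list: stratum, sex and age group named, treatment absent. Treatment is extracted into the dataset, and the MNAR step describes borrowing from placebo as a departure, which makes most sense if active-arm data otherwise inform active-arm imputation. The code that would settle it is in a document not available here. All of this stands, and it is why the point is about an unstated step and not a demonstrated error.

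It is also fair to say that the practical effect is small. Only 4 of 246 patients failed to complete the epoch, the bias is conservative, and GLMM and logistic sensitivity analyses exist alongside. That stands too, with one reservation: completion is only a proxy, because SAP 5.1.2 also sets a month with fewer than 14 diary days to missing.

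A reader might infer a larger loss by supposing that imputed patients have no post-baseline data. Without covariates the difference would then be (1 − m) × 20, a loss of 1.0 point at 5%, 2.0 at 10% and 4.0 at 20%. The FAS definition rules this out: such patients are excluded (SAP 2.2 and the patient classification table in 5.5).

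**Conclusion.** The gap in SAP 5.4.3 is real: treatment is the one extracted covariate not named in the MAR step, and a run by arm is not stated. A programmer who follows the text literally would pool the arms and bias both MAR analyses towards no difference. For FAS patients the loss on a 20-point responder difference is about 0.05-0.2 points at 1.6% missing, 0.2-0.5 at 5%, 0.4-0.9 at 10% and 0.6-1.8 at 20%. These sizes rest on the assumed correlation of 0.5-0.7, an equal shift at each visit and equal missingness in the arms.

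Three stronger readings are not supported. The documents do not establish that the imputation actually pools the arms. They do not make the MAR analysis the reference against which the MNAR result must be read; SAP 2.5.3 offers both as checks on robustness, and a shift of this size would not empty the comparison of meaning. The primary result is not touched, because missing month 3 data count as non-response there (SAP 2.5.2). This is a minor point about one set of sensitivity analyses.

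**What to change.** Add one sentence to the MAR step of SAP 5.4.3. It should say either that the imputation is run separately by randomised arm (`BY trt01pn`), or that `trt01pn` is a predictor in the FCS models for `wk4`, `wk8` and `wk12`. Either removes the dilution. A run by arm also lets the visit correlations differ between arms, but fits each model on about half the data; adding treatment as a predictor keeps the full sample in each model and still allows a different effect at each visit.

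Then check the SAS code in the TFLs document against that sentence. If the code already does this, only the text changes. If it pools the arms, the code needs about one line and the MAR outputs need a rerun. No other analysis is affected.

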5.5 Rule of exclusion criteria of analysis sets

The protocol deviations during screening, baseline and treatment periods are defined below (Table 10). The deviation ID, deviation code and it's corresponding text description are

explained in Table 9. Patients exclusion based on protocol deviations and non- protocol deviations criteria are in Table 11.

Table 8 Deviation Codes Description

Deviation code	Text description	Deviation ID
1	SELECTION CRITERIA NOT MET	INCLXX ; EXCLXX
2	PATIENT NOT WITHDRAWN AS PER PROTOCOL	WITHXX
3	PROHIBITED CONCOMITANT MEDICATION	COMDXX
4	TREATMENT DEVIATION	TRTXX
998	OTHER	OTHXX

Table 9 Protocol Deviations

Deviation ID	Description of Deviation
Scr INCL01	Informed consent not signed.
Scr INCL02	Adults <18 to >65 years of age
Scr INCL03	Documented history of migraine (with or without aura) for less 12 months prior to screening according to the International Classification of Headache Disorders-3rd Edition (ICHD-3)
Scr INCL04	< 4 or ≥15 days per month (in at least two separate attacks) of migraine symptoms (based on ICHD-3 criteria) on average across the 3 months prior to screening based on retrospective reporting
Scr INCL05	≥15 days per month of headache symptoms (ie migraine and non-migraine)
Scr INCL06	Not failed 2 to 4 prior migraine prophylaxis treatments out of the following: 
 Propranolol/metoprolol, topiramate, flunarizine, valproate/divalproex, amitriptyline, venlafaxine, lisinopril, candesartan, locally approved products (e.g. oxeterone or pizotifen)
Scr INCL07	Failed one and failed Or not be suitable for a second of the following: Propranolol or Metoprolol, Topiramate, Flunarizine
Scr INCL08	Failed or not be suitable for Valproate or Divalproex
Bln INCL09	Migraine frequency interval out of 4 to 14 migraine days during the Baseline Epoch, confirmed by the eDiary
Bln INCL10	<80% eDiary compliance during the Baseline Epoch
Scr EXCL01	To be older than 50 years of age at migraine onset
Scr EXCL02	To be unable to differentiate migraine from other headaches
Scr EXCL03	History of cluster headache or hemiplegic migraine headache

Deviation ID	Description of Deviation
Scr EXCL04	Failed more than 4 prior migraine prophylaxis treatments out of the following: Propranolol/metoprolol, topiramate, flunarizine, valproate/divalproex, amitriptyline, venlafaxine, lisinopril, candesartan, locally approved products (e.g. oxeterone or pizotifen)
Scr EXCL05	Use of a prophylactic migraine medication within 5 half-lives, or a device or procedure within one month prior to the start of the baseline phase or during the baseline phase
Scr EXCL06	Prior Botulinum toxin A treatment in the head/neck region (including cosmetic use or other licensed indications for Botox [®]) within 4 months prior to randomization
Scr EXCL07	Use of the following for any indication in the 1 month prior to the start of the baseline phase or during the baseline phase: Ergotamines or triptanes ≥ 10 days/month, or Simple analgesics (NSAIDs, acetaminophen, paracetamol) ≥ 15 days/month, or Opioid- or butalbital-containing analgesics ≥ 4 days/month
Scr EXCL08	Anticipated to require any excluded medication, device or procedure (e.g., nerve block, occipital nerve stimulators, transcranial magnetic stimulation) during the study
Scr EXCL09	Active chronic pain syndromes (e.g., fibromyalgia or chronic pelvic pain)
Scr EXCL10	History or current evidence of major psychiatric disorder (such as schizophrenia, bipolar disorder or type B personality disorder that might interfere with the ability to properly report clinical outcomes)
Scr EXCL11	Evidence of drug or alcohol abuse or dependence within 12 months prior to screening, based on medical records or patient self-report
Scr EXCL12	Current evidence of depression based on a BDI-II total score of > 19 at screening. Patients with anxiety disorder and/or major depressive disorder are permitted in the study if they are considered by the investigator to be stable and are taking no more than one medication per disorder. Patients must have been on a stable dose within the 3 months prior to the start of the baseline phase
EXCL12B	██████ assessment was not performed during the screening and baseline epoch
Scr EXCL13	History of seizure disorder or other significant neurological conditions other than migraine
Scr EXCL14	C-SSRS exclusion criterion met. "yes" on Item 4 or 5 of C-SSRS, if this ideation occurred in the past 6 months, or "yes" on any item of the Suicidal Behavior section, except for the "Non-Suicidal Self-Injurious Behavior" (item also included in the Suicidal Behavior section), if this behavior occurred in the past 2 years

Deviation ID	Description of Deviation
Scr EXCL15	Myocardial infarction, stroke, transient ischemic attack, unstable angina, or coronary artery bypass surgery or other revascularization procedures within 12 months prior to screening
Scr EXCL16	History or current diagnosis of ECG abnormalities indicating significant risk of safety for patients participating in the study
Scr EXCL17	History of malignancy of any organ system (other than localized basal cell carcinoma of the skin or in situ cervical cancer), treated or untreated, within the past 5 years, regardless of whether there is evidence of local recurrence or metastases
Scr EXCL18	Hepatic disease by history or total bilirubin $\geq 2 \times$ ULN or ALT or AST $\geq 3 \times$ ULN as assessed by central laboratory at initial screening
Scr EXCL19	Pregnant or nursing (lactating) women
Scr EXCL20	Women of child-bearing potential, defined as all women physiologically capable of becoming pregnant, unless they are using highly effective methods of contraception during dosing and for 110 days after stopping of study medication
Scr EXCL21	Use of other investigational drugs within 5 half-lives of enrollment, or until the expected pharmacodynamic effect has returned to baseline, whichever is longer
Scr EXCL22	History of hypersensitivity to the study drug or its excipients
Scr EXCL23	Any prior exposure to investigational products targeting the CGRP pathway, including previous AMG 334 studies
Scr EXCL24	Unlikely to be able to complete all protocol required study visits or procedures, and/or to comply with all required study procedures (e.g., independent completion of electronic diary items) to the best of the patient's and investigator's knowledge
WITH01	Emergence of certain adverse events, such as malignancy, elevated ALT or AST, liver failure or serious chronic infection and treatment was not discontinued
WITH02	Protocol violation that results in a significant risk to the patient's safety but treatment was not discontinued
TRT01	Patient received damaged or expired study drug
TRT02	Subject missed dosing at two consecutive visits.
TRT03	Subject was randomized but did not receive any study drug
TRT04	Subject received study drug without being randomized into study
TRT06	Partial dose administered
TRT07	Study drug mishandled

Deviation ID	Description of Deviation
TRT08	Patient randomised in wrong strata
COMD01	All oral beta blockers, Topiramate, Flunarizine, Valproate/Divalproex, Antidepressants (amitriptyline, venlafaxine, desvenlafaxine), ACE/ARB (lisinopril, candesartan), Serotonin antagonistic agents (oxetorone, pizotifen, methysergide)
COMD02	Botulinum toxin (in the head and/or neck region)
COMD03	Invasive interventions throughout the study (eg, nerve blocks, occipital nerve stimulators, transcranial magnetic stimulation)
OTH07	Informed consent was signed after the patient entered the study
OTH12	Non-compliance with ICH GCP

Table 10 Patient Classification

Analysis Set	PD ID that cause patients to be excluded	Non-PD criteria that cause patients to be excluded
RAS	NA	Not randomized;
FAS	NA	Mistakenly randomized and no double-blind study drug taken; No post-baseline measurement in primary efficacy endpoint during DBTE;
SAF	NA	No double-blind study drug taken;

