9.1 Analysis sets

The Full analysis set (FAS) will consist of all patients who started study medication and have completed at least one post-baseline monthly migraine day measurement in the double-blind treatment epoch. In FAS, patients will be analyzed according to randomized treatment, regardless of the actual treatment received.

The Safety analysis set (SAF) will consist of all randomized patients who received at least one dose of investigational product and will be analyzed based on actual treatment received.

The open-label analysis set (OLAS) will consist of all patients receiving at least one dose of AMG 334 in the open-label treatment epoch. This analysis set will be used when summarizing data collected during the Open-Label Treatment Epoch.

The PTA analysis set (PTAS) will consist of a subset of OLAS patients receiving at least one dose of AMG 334 in the PTA-Open-Label Treatment Epoch.

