2.2 Analysis sets

The **Randomized Analysis Set** (RAS) will consist of all participants who received a randomization number, regardless of receiving study medication.

The **Full Analysis Set** (FAS) will consist of all participants who started study medication and have completed at least one post-baseline monthly migraine day measurement in the doubleblind treatment epoch. In FAS, subjects will be analyzed according to randomized treatment, regardless of the actual treatment received. Analyses for efficacy endpoints and patient reported outcomes (PROs) will utilize this analysis set.

The **SAFety analysis set** (SAF) will consist of all randomized subjects who received at least one dose of investigational product and will be analyzed based on actual treatment received. Analyses for safety endpoints and summary of IP administration will utilize this analysis set. Rule of exclusion criteria of analysis sets is presented in [Appendix 5.5](#).

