2.5 Analysis of the primary objective

2.5.1 Primary endpoint

The primary endpoint is the achievement of at least a 50% reduction from baseline in monthly migraine days in the last month (month 3) of the Double-Blind Treatment Epoch.

The primary analysis will contrast active investigational drug versus placebo in the FAS.

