2.5.2 Statistical hypothesis, model, and method of analysis

The following hypothesis refers to alternative hypothesis. For tests of superiority, null hypothesis presuppose no difference between the treatment groups with respect to the parameter of interest.

Primary hypothesis

- The active treatment arm group is superior to placebo with regard to the proportion of patients who achieve at least a 50% reduction from baseline in monthly migraine days in the last month (month 3) of the Double-Blind Treatment Epoch;

$$H_1: \theta_1 > 1$$

where θ_1 is the odds ratio of active over corresponding placebo.

The primary analyses will compare the 50% response rate, which is defined as the proportion of patients who achieve at least a 50% reduction from baseline in monthly migraine days in the last month (month 3) of the Double-Blind Treatment Epoch, between AMG 334 vs placebo. Patients with missing monthly migraine days' data at month 3 of the double-blind treatment epoch will be imputed as non-responders.

A Cochran-Mantel-Haenszel (CMH) test stratified by the migraine frequency (4-7 and 8-14 monthly migraine days strata) will be used under a significance level of 0.025, one-sided (0.05, two-sided) to evaluate the association between the 50% responder rate and the treatment. The estimated common odds ratio, 95% confidence intervals and two-sided p-values will be reported.

Additionally, the estimated common relative risk and risk difference with their asymptotic (Wald) confidence limits will be provided.

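### The FAS exclusion row in SAP Table 10 is worded differently from the FAS definition in SAP 2.2 and, read literally, would drop patients whom SAP 2.5.2 counts as non-responders

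*SAP*

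**What the plan says.** SAP 2.2 admits to the FAS participants who "started study medication and have completed at least one post-baseline monthly migraine day measurement" in the double-blind epoch. Protocol 9.1 sets the same condition, that patients "have completed at least one post-baseline monthly migraine day measurement in the double-blind treatment epoch". Neither text names a month.

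SAP 2.2 closes with a pointer: "Rule of exclusion criteria of analysis sets is presented in" Appendix 5.5. The patient classification table there (captioned Table 10) gives two FAS exclusions that are not based on protocol deviations: "Mistakenly randomized and no double-blind study drug taken" and "No post-baseline measurement in primary efficacy endpoint during DBTE". The deviation column for the FAS is marked not applicable.

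SAP 2.5.1 defines the primary endpoint as a reduction of at least 50% in monthly migraine days in the last month of the epoch, month 3, and runs the primary analysis in the FAS. SAP 2.5.2 adds that patients with missing monthly migraine day "data at month 3 of the double-blind treatment epoch will be imputed as non-responders". Protocol 9.4.2 has the same rule.

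**The concern.** The two FAS rules use different yardsticks. SAP 2.2 asks for a monthly migraine day value at any month. Table 10 asks for a measurement of the primary endpoint, which the SAP defines at one month only. A dosed patient with usable diary data in months 1 and 2 and none in month 3 is in the FAS under 2.2 and, on the literal wording, out of it under Table 10. Yet 2.5.2 keeps this same patient as a non-responder.

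The denominator of the primary test is at stake. Under the literal rule every FAS patient has a month 3 value, so the non-responder rule has nobody to act on. Patients who stop early leave the comparison instead of counting as failures.

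The same row has a second, smaller mismatch. It excludes an undosed patient only if that patient was randomized by mistake, whereas 2.2 requires that study medication was started. The SAF row of the same table lists absence of double-blind drug with no such qualifier.

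**Working it through.** **Texts side by side, for a dosed patient with month 1 and 2 values but no month 3 value**

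| Source | Result |
|---|---|
| Protocol 9.1, SAP 2.2 | In the FAS |
| SAP 2.5.2, Protocol 9.4.2 | Non-responder in the primary analysis |
| Table 10, literal (endpoint = month 3) | Out of the FAS |
| Table 10, broad (no value at any DBTE month) | In the FAS |

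**The plan's own figure.** SAP 3 and Protocol 9.8 give 110 per arm, two-sided alpha 0.05, 90% power, 18% on placebo and about 20 points more on active (38%), odds ratio 2.8.

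- Odds ratio: (0.38/0.62)/(0.18/0.82) = 2.79.
- Power: [0.20 − 1.96·√(2·0.28·0.72/110)] / √((0.18·0.82 + 0.38·0.62)/110) = (0.2000 − 0.1187)/0.0590 = 1.378, giving 91.6%. Subtracting a continuity correction of 1/110 from the difference gives 89.0%.

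The stated 90% therefore reproduces closely, and the sample size is not in dispute.

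**Difference between the two readings.** Assume 38% and 18% are the response rates in patients with month 3 data. Let m1 and m0 be the shares of active and placebo patients without a month 3 value who would be in the FAS under 2.2.

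- Literal exclusion: difference = 0.38 − 0.18 = 20.0 points, odds ratio 2.79, whatever m1 and m0 are.
- SAP 2.2 with non-responder imputation: difference = 0.38(1 − m1) − 0.18(1 − m0).

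The only documented rate is in the Protocol's Amendment 3 rationale: 246 randomized and 242 completing the double-blind epoch, so 4/246 = 1.6%. The arms of these four are not given, so the one-arm rows assume 123 per arm (4/123 = 3.3%). Every rate marked "assumed" is an assumption of this review.

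| Missing, active / placebo | Calculation | Difference with imputation | Odds ratio |
|---|---|---|---|
| 1.6% / 1.6% (documented total, assumed balanced) | 0.3738 − 0.1771 | 19.7 points | 2.77 |
| 3.3% / 0% (all four on active, assumed) | 0.3676 − 0.1800 | 18.8 points | 2.65 |
| 0% / 3.3% (all four on placebo, assumed) | 0.3800 − 0.1741 | 20.6 points | 2.91 |
| 5% / 5% (assumed) | 0.3610 − 0.1710 | 19.0 points | 2.74 |
| 8% / 2% (assumed) | 0.3496 − 0.1764 | 17.3 points | 2.51 |
| 5% / 10% (assumed) | 0.3610 − 0.1620 | 19.9 points | 2.92 |

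Against 20.0 points and 2.79, the gap is 0.3 points at the documented rate if balanced, 1.0 at 5% per arm and 2.7 at 8%/2%. With more missing on placebo, the odds ratio under imputation exceeds the complete-case one.

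**The 1.6% is not a ceiling.** SAP 5.1.2 sets a month to missing when it has fewer than 14 diary days, so a completer can lack a month 3 value. SAP 2.3.1 also counts as a completer someone who misses the week 12 assessment but enters open label. Conversely, the four non-completers need not all lack a month 3 value.

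**The case against.** The strongest reply is that the literal reading is not the natural one. If Table 10 meant month 3 only, its references to post-baseline and to the whole double-blind epoch would add nothing, since month 3 is always both. The SAP also handles the responder measure across visits: Table 5 asks for by-visit summaries of the primary endpoint and a mixed model over scheduled visits. SAP 2.5.3 examines missing primary data and repeats the stratified test under MAR and MNAR imputation, and 5.1.6 sets a trigger for more than 20% missing at week 12. All this, and the non-responder rule itself, presupposes FAS patients without a month 3 value.

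This stands. A reader might infer from Table 10 that the plan specifies a completer analysis, but the documents taken together do not support that. They support a row that can be misapplied. One strand is weaker than it looks: the sentence in 5.1.6 on imputing non-response at each time point is written for a secondary endpoint, and the same section ties missing primary data to week 12.

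A further reply is that 2.2 already contains a full inclusion definition, so nobody would program from Table 10 alone. That limits the risk without removing it, because 2.2 itself names the appendix as the place for the exclusion rule.

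On undosed patients, the SAP change log explains the qualifier: it was added to make clear that mistaken randomization by itself does not remove a patient from the FAS. As 2.2 already requires that treatment was started, this mismatch is minor.

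**Conclusion.** The wording conflict is real and should be removed. Table 10 does not match SAP 2.2 or Protocol 9.1, and its literal form would turn the primary analysis into a month 3 complete-case analysis and leave the non-responder rule idle. The documents do not show that this was intended or programmed.

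The likely size is small: about 0.3 points on a 20-point difference at the documented non-completion if balanced, and 1.0 to 2.7 points in the assumed scenarios of 5% per arm and 8%/2%. These figures rest on 38% and 18% holding among patients with month 3 data and on missing rates that, apart from the 1.6%, are assumed.

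A reader might also infer that literal exclusion always flatters the drug. It does not. The direction depends on which arm has more missing month 3 values, and the documents do not report that.

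**What to change.** Reword the FAS row of Table 10 so that it is the exact negative of SAP 2.2: exclude a patient who took no double-blind study drug, or who has no monthly migraine day value after baseline at any month of the DBTE. Drop the qualifier about mistaken randomization from this row. If the point in the change log is still wanted, put it in a separate note saying that mistaken randomization alone does not exclude a dosed patient. Add one sentence stating that a missing month 3 value alone never removes a patient from the FAS. The sponsor should also confirm which rule the analysis programs use.

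The cost is a few lines of SAP text and one check of the FAS flag. No new method or data are needed, since the change restores what Protocol 9.1 and SAP 2.2 and 2.5.2 already specify. If the literal rule was programmed, the estimate could shift slightly in either direction.
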